CRITIC

Pilot study

Coated devices to decRease InfecTion in the ICu Statistical Analysis Plan

Chief Investigators:

[name], PhD

[name], PhD

Statistician

[name] [name]

Sponsor:

Bactiguard AB, Tullinge, Sweden

Sponsor representative:

[name], PhD

Research Institute, HCor - Hospital do Coração, São Paulo, Brazil

SUMMARY

| | |
|---|----|
| 1. Administrative information..... | 4 |
| 2. Aim and objectives | 5 |
| 2.1) Objectives..... | 5 |
| 3. Study methods | 6 |
| 3.1) Trial design | 6 |
| 3.2) Method of randomization and concealment allocation | 6 |
| 3.3) Outcomes | 6 |
| 3.4) Sample size..... | 8 |
| 4. Analyses set..... | 9 |
| 4.1) Per Protocol Set..... | 9 |
| 4.2) Full compliance set..... | 9 |
| 5. Analyses Methods | 9 |
| 5.1) Baseline characteristics..... | 9 |
| 5.2) Primary outcome..... | 10 |
| 5.3) Exploratory outcomes | 10 |
| 5.4) SOFA | 10 |
| 5.5) Subgroup analysis..... | 11 |
| 5.6) Safety and Adverse Events..... | 11 |
| 5.7) Missing data and imputation | 11 |
| 6. Statistical software | 12 |
| REFERENCES | 13 |

ABBREVIATIONS

| | |
|-------|--|
| AE | adverse event |
| ATB | antibiotics |
| CAUTI | catheter related urinary infection |
| CRBSI | catheter related bloodstream infection |
| CVC | central venous catheters |
| ICU | intensive care unit |
| ETT | endotracheal tubes |
| UC | urinary foley catheters |
| RR | risk ratio |
| SAP | statistical analysis plan |
| SOFA | sequential organ failure assessment |
| VAP | ventilator associated pneumonia |

1. Administrative information

Statistical Analysis Plan (SAP) for the CRITIC Pilot Study (Coated devices to decrease Infection in the ICU).

- ClinicalTrials.org Registration: NCT03868241
- Protocol Version 2.0 – January, 2019.
- SAP Revision:

| SAP version | Protocol Version | Description and Reason for Change | Date |
|--------------------|-------------------------|--|-------------|
| 1.0 | 2.0 | Not Applicable | 03/10/2019 |

2. Aim and objectives

The full rationale for undertaken the trial is explained in detail in the Protocol. Briefly, CRITIC is a pilot study to assess feasibility and potential recruitment rate for a larger trial using coated (Bactiguard®) devices in critically ill patients. And establish the incidence of ICU-acquired sepsis in the most severe critically ill patients in Brazil.

2.1) Objectives

Primary objectives:

- To assess feasibility of the simultaneous insertion of coated and uncoated ETT, CVC and UC in recently admitted critically ill patients without previous invasive devices in a randomized controlled trial.
- To determine how many patients admitted to the ICU will require CVC, ET and UC insertion and, of those, how many will develop sepsis from 48 hours after randomization until day 28 after randomization or until ICU discharge.

Secondary objectives (clinical outcomes):

- Occurrence of nosocomial sepsis up to 28 days after randomization in control (uncoated devices) versus intervention (coated devices) groups
- Combined endpoint of any of the following infections occurring during ICU stay: Ventilator associated pneumonia (VAP), Catheter related bloodstream infection (CRBSI) and Catheter associated urinary tract infection (CAUTI).
- Occurrence of each nosocomial infection individually (VAP, CRBSI, CAUTI) in both groups and rates of positives cultures at each site.
- ICU and Hospital mortality in both groups.

3. Study methods

The full methods section, including detailed intervention and eligibility (inclusion and exclusion criteria), is explained in the Protocol.

3.1) Trial design

Pilot exploratory, randomized, open label, controlled trial. Critically ill patients which will demand placement of invasive devices for organ support (endotracheal tube, central venous catheter and urinary Foley catheter) will be randomized 1:1 to receive coated (Bactiguard®) or habitual (non-coated) devices.

3.2) Method of randomization and concealment allocation

Randomization list will be electronic generated using appropriate software and will be done in blocks stratified by site and by the presence of sepsis at randomization. Allocation group will only be informed after patient register in the electronic database, thereby preventing the investigator of anticipating for which group the patient will be randomized. Due to technical reasons, there will be no blinding.

3.3) Outcomes

The analysis of the two main outcomes involves both the feasibility of the study and the need to obtain epidemiological data on the occurrence of nosocomial sepsis after ICU admission. The feasibility will be assessed by study recruitment rate and by local input on the challenges of the randomization process. We expect a recruitment rate of approximately 1.3 patients a month per site.

Sepsis will be defined as the occurrence of infection plus presence of organ failure, assessed by the Sequential Organ Failure Assessment (SOFA) score (Singer, JAMA 2016; Vincent, Intensive Care Med 1996). The presence of infection with an increase in SOFA score in at least two points will be considered as sepsis (Singer,

JAMA 2016). Sepsis will be further classified as probably related to devices or non-related to the devices after adjudication. Sepsis non-related to the devices will be those where an obvious source of infection that is not related to the devices and is present at device insertion or when the time between device insertion and sepsis diagnosis is less than 48 hours. Obvious sepsis sources unrelated to the devices include: Meningitis, soft tissue infections away from the puncture site (i.e., necrotizing fasciitis), intrabdominal infection and surgical wound infection. An introduction of a new antibiotic class will be used to trigger investigation.

VAP will be defined considering the classic diagnostic criteria (Kalanuria, Crit Care 2014):

1. New or progressive radiographic consolidation or infiltrate. In addition, at least 2 of the following:
 - a. Temperature $> 38^{\circ}\text{C}$
 - b. Leukocytosis (white blood cell count $\geq 12,000 \text{ cells/mm}^3$) or leukopenia (white blood cell count $< 4,000 \text{ cells/mm}^3$)
 - c. Presence of purulent secretions

CRBSI will be defined if **one** of the following is present plus criteria for identifying the catheter as the source (ECDC, 2013):

1. Patient has a recognized pathogen cultured from one or more blood cultures, and the pathogen is not related to an infection at another site.

OR

2. Patient has at least one of the following signs or symptoms: fever ($>38.0^{\circ}\text{C}$), chills, or hypotension, and the pathogen is not related to an infection at another site or, if the organism is a common commensal, it must be present from two or more blood cultures drawn on separate occasions. **AND**

3. Culture of the same organism from both the catheter tip and at least one percutaneous blood culture
4. Culture of the same organism from at least two blood samples (one from a catheter hub and the other from a peripheral vein or second lumen) meeting criteria for quantitative blood cultures (at least 5 times greater in

7(13)

catheter blood) or differential time to positivity (at least 2 hours earlier in catheter blood).

Therefore, for CRBSI to be diagnosed, patient must have criteria 1 OR 2 plus 3 OR 4.

Finally, CAUTI will be defined if **all** the following are present (Nicolle, Antimicrob Resist Infect Control 2014):

1. One or more organisms are present at quantitative counts $\geq 10^5$ colony-forming units/mL from an appropriately collected urine specimen
2. The attending physician believes there is an acute infection and prescribes antibiotics
3. There is no other plausible source of infection at the time the diagnosis of CAUTI is made

The number of antibiotic free days at 28 days will be defined as 28 less the number of days the patient received antibiotics.

All events will be adjudicated by the coordinating center.

3.4) Sample size

This is a pilot study including 100 unique patients. The density of incidence of sepsis and other device-related infection (VAP, CRBSI and CAUTI) will be calculated as the number of events over the total number of patients/day at risk. For the primary outcome of incidence of sepsis, this sample size will be able to inform 95% credible intervals with approximately 3 events per 100 patient-days overall (4 events per patient-day per group), and interval length based on Bayesian *Poisson* regression model with intercept parameter assuming non-informative normal prior centered in 8 event per 100 patient-days incidence rate, $N(e^{0.08}, 5)$.

The prior has a very large standard deviation, giving virtually no importance to its average choice, which was established assuming a slightly worse scenario than was described for a European population of 5 events per 100 patient-days (Allegranzi, 2011).

4. Analyses set

Study protocol mentioned that analysis will be done considering the intention to treat principle. However, during study conduction, some randomized patients did not require simultaneous insertion of all three devices (ETT, CVC and UC) due to illness severity, or the attending physician decided not to insert the devices. Those cases were excluded from the analyses. Consequently, main analysis will be carried out considering a Per Protocol Set (PPS) above. Our expectations are that per protocol and full compliance sets will be the same. Nevertheless, if it happens otherwise, full compliance set must be used to evaluate efficacy measures (infection incidences) and per protocol set to evaluate security measures (adverse events).

4.1) Per Protocol Set

All patients that were randomized, fulfill all inclusion and exclusion criteria, and receive the three devices (ETT, CVC and UC) from allocated arm (coated or habitual) at least one time.

4.2) Full compliance set

All patients that were randomized, fulfill all inclusion and exclusion criteria, and receive the three devices (ETT, CVC and UC) from allocated arm (coated or habitual) all the times that were needed.

5. Analyses Methods

Continuous data will be reported as mean (standard deviation) or median (quartiles) as appropriate. Categorical variables will be described by absolute and relative frequencies.

5.1) Baseline characteristics

Patients' baseline characteristics will be presented without any hypothesis test comparing patients allocated to Coated versus Habitual devices.

5.2) Primary outcome

As described at section 3.4 (sample size), the primary outcome of incidence of sepsis, will be estimated via Bayesian *Poisson* regression model with intercept parameter assuming non-informative normal prior centered in 8 event per 100 patient-day incidence rate, $N(e^{0.08}, 5)$.

5.3) Exploratory outcomes

The same Bayesian *Poisson* regression model with intercept parameter assuming non-informative normal prior centered in 8 event per 100 patient-day incidence rate, $N(e^{0.08}, 5)$, will be done to estimate other infection incidences (VAP, CRBSI, CAUTI).

Besides, the same model will be used to compare patients that used coated devices versus habitual devices. Results will be reported as Risk Ratios (RR) with 95% Credible Intervals. Models will be adjusted for admission type, baseline SOFA and the stratification variable (presence of sepsis at randomization).

Results will be reported considering adjudicated events and events reported by the centers. Sepsis, as reported by centers will be considered as: two point increase in SOFA plus newest use of ATB. The end of sepsis will be considered at the time of ATB withdrawal concomitant with any improvement in SOFA.

Based on those models, we will run simulations to explore scenarios for a larger trial.

5.4) SOFA

We intent to evaluate SOFA during ICU stay using hierarchical Bayesian linear regression models assuming intercept and slope hierarchical effects to patient to include individual time dependence, adjusted for baseline SOFA, and interaction of time and allocated device (coated or habitual). All priors shall be non-informative Normal distributed.

We may also test some nonlinear relation of SOFA on time in each group using polynomial or natural cubic splines. And evaluate alternatives to control death censoring (REF - <http://dx.doi.org/10.1136/bmj.j5748>) if mortality seems different between arms.

Results will be presented with proper graphs to highlight SOFA variation on time.

5.5) Subgroup analysis

Subgroup analysis will be tested by including interaction effect parameter into the model previously described in section 5.3. The only planned subgroup variable is the stratification characteristic: presence/absence of sepsis at admission.

5.6) Safety and Adverse Events

All reported Safety and Adverse events as described in the protocol will be presented with absolute and relative frequencies and tested with regular Fisher exact test between study groups (Coated vs. Habitual devices).

5.7) Missing data and imputation

We expect minimal missing data; none data imputation is planned.

6. Statistical software

Analyses will be done using R software (R Core Team, 2019). Bayesian models will be adjusted using *rstan* package (Stan Development Team, 2019).

REFERENCES

Nicolle LE. Catheter associated urinary tract infections. *Antimicrob Resist Infect Control*. 2014 Jul 25;3:23

Stan Development Team (2019). RStan: the R interface to Stan. R package version 2.19.2. <http://mc-stan.org/>.

R Core Team (2019). R: A language and environment for statistical computing. R Foundation for Statistical Computing, Vienna, Austria. URL <https://www.R-project.org/>.

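### The first primary objective is feasibility of inserting three devices simultaneously, but no planned measure would show how often randomised patients did not receive all three

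*SAP*

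**What the plan says.** Section 2.1 of the SAP gives as the first primary objective: "To assess feasibility of the simultaneous insertion of coated and uncoated ETT, CVC and UC in recently admitted critically ill patients without previous invasive devices".

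Section 3.3 states how feasibility is to be judged: "The feasibility will be assessed by study recruitment rate and by local input on the challenges of the randomization process". The only figure attached is an expectation, not a criterion: "We expect a recruitment rate of approximately 1.3 patients a month per site".

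Section 4 reports what happened during the trial: "some randomized patients did not require simultaneous insertion of all three devices (ETT, CVC and UC) due to illness severity". For other patients, the reason given is a physician's choice against insertion. The handling of both kinds of case is stated next: "Those cases were excluded from the analyses". As a result, "main analysis will be carried out considering a Per Protocol Set (PPS) above".

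Section 4.1 admits to that set only patients who received all three devices from their allocated arm at least once. Section 5.2, on the primary outcome, deals with sepsis incidence alone. No other part of section 5 analyses feasibility.

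**The concern.** An objective about inserting three devices at the same time needs a measure of insertion. Recruitment rate describes how quickly patients enter the trial, and the site input is tied to the randomisation process. Neither says what share of randomised patients went on to receive all three allocated devices.

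The patients described in section 4 carry the most direct information on this question. They were randomised on the expectation that all three devices would be needed, and that expectation was not met. The SAP mentions them only to explain why they leave the analyses. It plans no count, no proportion, no split by arm and no table of reasons.

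This matters because the pilot exists to inform a larger trial. Non-insertion after randomisation determines how many patients that trial must randomise for each one treated as intended. The trial is also open label, so a physician's decision not to insert could differ between arms, and no comparison by arm is planned.

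The point is separate from the choice of analysis set for infection rates. Analysing infections by intention to treat would still leave insertion unmeasured.

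**Working it through.** **Step 1. Match each stated measure to the objective.**

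| SAP item | What it measures | Shows non-insertion? |
|---|---|---|
| 3.3 recruitment rate | Patients entering per site-month; numerator not defined | No |
| 3.3 local input | Narrative on the randomisation process | Perhaps anecdotally; no denominator |
| 2.1 second primary objective | ICU admissions needing the three devices, and sepsis among them | No; it concerns need among admissions, not receipt among those randomised |
| 5.2 primary outcome | Sepsis incidence | No |
| 4.1 Per Protocol Set | Membership requires all three allocated devices at least once | No; the share is 100% by construction |

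Section 4.1 sets no timing condition. Simultaneity, which the objective names, is therefore not measured even among the patients who are kept.

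**Step 2. There is no figure of the plan's own to reproduce.** The SAP gives neither a number of non-insertions nor a target proportion.

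**Step 3. What the missing proportion would look like.** The number of non-insertions, *k*, is assumed. With n = 100 randomised, the proportion is (100 − *k*)/100 with an exact (Clopper-Pearson) 95% interval.

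| *k* per 100 randomised (assumed) | Received all three | 95% CI |
|---|---|---|
| 5 | 95% | 88.7 to 98.4 |
| 10 | 90% | 82.4 to 95.1 |
| 20 | 80% | 70.8 to 87.3 |

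Section 3.4 does not say whether its 100 patients are randomised or analysed. If 100 are analysed and 5, 10 or 20 more were randomised and removed, the proportions are 100/105 = 95.2%, 100/110 = 90.9% and 100/120 = 83.3%.

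**Step 4. Consequence for recruitment, if 1.3 per site-month counts randomised patients.** The rate of patients receiving all three devices is 1.3 × proportion:

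- *k* = 5: 1.3 × 0.95 = 1.24
- *k* = 10: 1.3 × 0.90 = 1.17
- *k* = 20: 1.3 × 0.80 = 1.04

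The reported recruitment rate would be 1.3 in every row. If 1.3 instead counts only patients who received all three, this discount does not apply. The randomisation rate would then be higher: 1.3/0.95 = 1.37 to 1.3/0.80 = 1.63.

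**Step 5. Consequence for a larger trial.** The number randomised per patient treated as intended is 1/proportion: 1/0.95 = 1.05 to 1/0.80 = 1.25, or about 5% to 25% more.

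**The case against.** A reader might infer three stronger claims that the SAP does not support.

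- *That the pilot is unable to report failure on this objective, or hides it.* Section 4 openly states that these patients existed and gives two reasons. Nothing forbids counting them, and a participant flow diagram could supply the number. What is missing is a planned measure.
- *That insertion failed.* The SAP records devices not required, or a physician's decision not to insert. It records no unsuccessful insertion. These cases bear on feasibility through the judgement of need at randomisation; they do not show that insertion is technically infeasible.
- *That the recruitment rate definitely counts randomisations.* Section 3.3 does not define its numerator, so the discounted rates hold only on that reading.

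Other arguments on the plan's side also have weight. Recruitment rate is a legitimate aim, since section 2 names it alongside feasibility. Local input could bring up the problem informally. Section 4 assigns analysis sets to infection and adverse-event measures and none to feasibility, so its exclusion may have been meant for outcome analyses only. The 100% in the Per Protocol Set is then a figure nobody plans to calculate; it shows only that this set cannot answer the question. The protocol, which is not at hand, may hold a feasibility criterion.

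These arguments limit the wording and the severity but do not close the gap. Section 3.3 sets out what feasibility will be assessed by, and that list does not answer the objective in section 2.1. Narrative input gives no denominator, and a disclosed exclusion is not an outcome with an interval and reasons by arm.

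**Conclusion.** The concern holds as a mismatch within the SAP: the first primary objective is about simultaneous insertion, the stated feasibility measures are not, section 5 analyses no feasibility outcome, and the informative patients are excluded from the analyses. The conclusion goes no further than that no planned measure would show non-insertion.

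Its actual size is unknown because the SAP gives no count. The range of 5 to 20 per 100 is an assumption with no anchor in the document, and the recruitment figures rest on the further assumption that 1.3 counts randomised patients. The mismatch itself depends on neither. It should be fixed, as a cheap improvement to an exploratory pilot.

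**What to change.** 1. In sections 3.3 and 5.2, add a primary feasibility outcome: the proportion of all randomised patients who received all three devices from the allocated arm at the index insertion. Define the index insertion so that simultaneity is captured. Report the proportion overall and by arm, with a 95% interval.
2. Tabulate reasons for non-insertion by arm, using at least the two that section 4 already names (not required; physician decision) and a category for any other reason.
3. State in section 4 that every randomised patient stays in the denominator of this outcome, whatever set is used for infections and adverse events.
4. State whether the recruitment rate counts randomised patients or patients who received all three devices, and report both per site-month.
5. Use the observed non-insertion proportion as an input to the larger-trial simulations in section 5.3.

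The cost is SAP wording and one extra table. Section 4 shows that the cases and their broad reasons are already known. The downside for the sponsor is a feasibility figure that may look less favourable than recruitment alone.

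### Neither sepsis definition requires an infection distinct from the one at randomization or fixes the reference SOFA, so later worsening of admission sepsis can enter the primary incidence

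*SAP*

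**What the plan says.** **Target.** Section 2 says the pilot is to "establish the incidence of ICU-acquired sepsis in the most severe critically ill patients in Brazil". The primary objective in section 2.1 asks "how many will develop sepsis from 48 hours after randomization until day 28 after randomization or until ICU discharge". Section 3.3 also calls the outcome nosocomial.

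**Population.** Under section 3.2 randomization is "stratified by site and by the presence of sepsis at randomization", so patients who are already septic are enrolled.

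**Event, main version (3.3).** A general sentence comes first: "Sepsis will be defined as the occurrence of infection plus presence of organ failure". The operative rule follows: "The presence of infection with an increase in SOFA score in at least two points will be considered as sepsis". Starting a new class of antibiotic prompts an investigation. Adjudication then sorts sepsis into probably device-related and not device-related. The second label applies when an obvious unrelated source was already there at insertion, or when fewer than 48 hours separate insertion and diagnosis.

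**Event, centre-reported version (5.3).** The rule is "two point increase in SOFA plus newest use of ATB". The next sentence closes an episode: "The end of sepsis will be considered at the time of ATB withdrawal", provided SOFA has improved at the same time.

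**Rate (3.4 and 5.2).** Incidence is events divided by patient-days at risk. The primary outcome is the incidence of sepsis, not of device-related sepsis only.

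**The concern.** A patient septic at randomization already has an infection and organ dysfunction. If that infection progresses after 48 hours, SOFA rises by two points and the antibiotics are escalated, every written element of either definition can be met without any ICU-acquired infection. With no reference SOFA named, two programmers could also count different events from the same data.

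This matters in three places:

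- The primary rate could include continuation of sepsis that was not acquired in the ICU.
- Section 5.3 uses these models to simulate scenarios for a larger trial, so an inflated rate would carry forward.
- Such events sit by definition among patients septic at randomization, and section 5.5 names that factor as the only planned subgroup.

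**Working it through.** **1. The plan's own precision figure (for scale only; the point does not depend on it).** Section 3.4 gives an interval length of about 3 per 100 patient-days overall and 4 per group, with a prior centred at 8 per 100. Total patient-days T is not stated. With a near-flat prior, length ≈ 2 × 1.96 × √(rate/T), so T = rate × (2 × 1.96/0.03)².

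- At 8 per 100: T = 0.08 × 17,073 ≈ 1,366 (13.7 days per patient), or about 109 events.
- At 5 per 100, the published figure the SAP cites: T = 0.05 × 17,073 ≈ 854 (8.5 days per patient), or about 43 events.
- Per group, T halves and the length becomes 3 × √2 ≈ 4.2, in line with the stated 4.

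The stated precision is plausible, but it cannot be confirmed without T.

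**2. Does any text exclude continuation of admission sepsis?**

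- *48-hour start (2.1).* It removes early worsening only. The secondary between-group objective for nosocomial sepsis states no 48-hour start.
- *New antibiotic class (3.3).* It triggers investigation and is not part of the definition. Escalation for a failing admission infection would trigger it too.
- *Recent antibiotic use (5.3).* The same escalation satisfies it.
- *Device-related label (3.3).* It classifies events. Nothing says that unrelated events leave the primary incidence. Pneumonia and urinary sepsis present on admission are not among the listed unrelated sources, although the list may be open. The VAP criteria also accept a progressive infiltrate.
- *Adjudication (3.3).* It covers all events, but no written rule tells adjudicators to reject continuation of the infection present at randomization.
- *End-of-sepsis rule (5.3).* It could separate episodes, but it stands beside the centre-reported version only. It is not tied to the sepsis present at randomization, to event counting or to days at risk.

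**3. Does any text fix the reference SOFA?** No. Candidates are the randomization value, the previous day, the 48-hour value or the lowest value so far. Take a patient whose SOFA falls after randomization and then climbs two points without passing the randomization value. This is an event against the lowest value and no event against the randomization value.

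**4. Illustration of size, entirely on assumptions.** Let s be the share septic at randomization and q the share of those with one continuation event after 48 hours. The SAP gives neither. Extra events = 100 × s × q. With s from 30% to 70% and q from 5% to 30%:

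- lowest: 100 × 0.30 × 0.05 = 1.5; highest: 100 × 0.70 × 0.30 = 21;
- against 109 events (8 per 100, T = 1,366): +1% to +19%;
- against 43 events (5 per 100, T = 854): +3% to +49%.

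Each rate is paired with the T that it implies. The spread shows that no single figure is dependable.

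**5. Direction in the subgroup.** In the septic stratum, let new sepsis occur at rate λ under habitual devices and ρλ under coated devices. Let continuation events occur at rate κ in both arms, on the assumption that the devices do not affect an infection that predates them. The observed ratio is (ρλ + κ)/(λ + κ), which lies between ρ and 1. The septic stratum is pulled toward no effect and the non-septic stratum is not.

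**The case against.** The best reply is that the rule should not be read from one sentence. The general definition speaks of an occurrence of infection, the objective of patients who develop sepsis from 48 hours on, and section 3.3 of nosocomial sepsis; all three point to new onset. A new antibiotic class prompts investigation, every event is adjudicated, and infections with an obvious unrelated source at insertion are labelled as such. The end-of-sepsis rule suggests that an unresolved admission episode is still one episode. Section 3 refers the full methods to the protocol, and adjudication rules may sit there or in a charter. The arm comparison is exploratory, adjusted for baseline SOFA and sepsis at randomization, in a pilot of 100 patients.

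Much of this stands. A reader might infer that infection plus a two-point rise is all the plan needs, so that any worsening of admission sepsis counts as ICU-acquired. The SAP does not support that: worsening before 48 hours falls outside the primary window, and adjudicators may reject continuation of the same infection.

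What does not stand is that these safeguards close the gap. They state an intention, but none is written as a criterion that removes a continuation event. The SAP itself defines sepsis, its centre-reported variant and its end, so the missing elements belong beside those definitions or in a cited document. Covariate adjustment does not correct misclassified events.

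**Conclusion.** The point holds in a limited form. As written, the SAP does not exclude post-48-hour worsening of admission sepsis with antibiotic escalation from an outcome meant to be ICU-acquired, and it leaves the two-point rise without a reference. Such events can count; the SAP does not show that they all will.

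The direction is clear: any that are counted raise the primary rate and lie in the septic stratum. The size is not known. A reader might take one of the illustrated percentages as the expected bias, but the septic share and worsening rate are assumed and the patient-days are back-solved from the interval length. The conclusion rests on the SAP alone; a protocol or charter that already requires a distinct infection would reduce the remedy to a cross-reference. The SAP should be changed on this point, but the defect does not invalidate the pilot.

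**What to change.** Amend sections 3.3 and 5.3 so that both versions use the same rule:

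- **New infection.** Count an event only if the infection differs in site or organism from the one at randomization, or begins after that episode has met the SAP's own end-of-sepsis rule.
- **Reference SOFA.** Name one pre-specified value from which the two-point rise is measured.
- **Days at risk.** Match them to the event rule. Either a new-site or new-organism infection can count during the admission episode, and those days stay at risk; or days at risk start when the episode ends, and earlier events do not count. Mixing the two would give events with no exposure.
- **Adjudication.** Say that continuation of the infection at randomization is not an event, and whether sepsis labelled unrelated to the devices stays in the primary rate.

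**Cost.** This needs SAP wording and programming on the SOFA and antibiotic data the plan already uses. The site and organism of the admission infection must also be available, which the SAP does not confirm. Section 4 shows that recruitment had begun, so events already adjudicated may need a second look. Somewhat fewer events will be counted.

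The second days-at-risk option also loses exposure. If half the patients were septic and each lost 7 days (both assumed), 50 × 7 = 350 patient-days would go: 26% of 1,366, or 41% of 854. At an unchanged rate the interval length would grow from 3 to 3/√0.74 ≈ 3.5, or 3/√0.59 ≈ 3.9, per 100 patient-days. The first option avoids that loss.
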